7.6.1.4 ADHESIVE RESIDUE

The source data will be the adhesive residue scores of the patches. A summary of Adhesive Residue Scores recorded in clinic will present the adhesive residue scores with the number and percent of subjects by each treatment and time point. All adhesive residue data will be listed, including those captured in the dermal evaluation diary.

7.7 SAFETY ANALYSES

Safety data for the Dose-Optimization Period will be summarized using combined data from all subjects in the SP population.

Safety data from the double-blind Treatment Period will be summarized using data from each treatment arm where applicable in the SP population.

No inferential statistics are planned.

7.7.1 Adverse Events

Treatment-emergent adverse events will be assigned to either the open-label Dose-Optimization Period or the double-blind Treatment Period. TEAEs occurring in the safety follow up after the double blind Treatment Period will be reported under the double blind Treatment Period for the last treatment they received. TEAEs for which a missing or incomplete start and/or stop date makes it impossible to determine which period of the study they started in will be counted as starting in the Dose-Optimization Period. The subject's dose of study drug at the onset of the event will be determined for all TEAEs. If a missing or incomplete start date makes it impossible to determine the dose at onset, then the dose at onset will be set to the lowest dose in the study (i.e., 5 mg/ 4.76 cm²). Adverse events that start before the first patch application will be summarized separately. For summaries, TEAEs with missing severity are assumed to be severe, and TEAEs with missing relationship to study drug are assumed to be related.

Summary statistics for TEAEs will be presented separately for the SP population on all subjects combined during the Dose-Optimization Period and by treatment arm during the double-blind Treatment Period. All summaries of adverse events will consist of the number of events and the numbers and percentages of subjects who had the events being summarized.

All TEAEs will be classified by SOC and PT using the latest version of MedDRA dictionary. All TEAEs that occur after first patch application up to 30 days following last patch application will be summarized. Subjects may have more than one TEAE per SOC or PT. Unless otherwise specified, at each level of subject summarization in reporting the incidence of the AE, a subject will be counted once if the subject reported one or more events.

The following summaries will be presented separately for the Dose-Optimization Period and the double-blind Treatment Period by the dose being taken at the onset of the events and by MedDRA SOC, and preferred term:

- Overall summary of TEAEs
- TEAEs
- Treatment-related TEAEs
- TEAEs leading to premature discontinuation of study drug
- TEAEs by intensity.

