## **5 INVESTIGATION PLAN**

### **5.1 Study Design**

This is a randomized, double-blind, cross-over, placebo controlled study to evaluate the safety and efficacy of d-ATS (5 mg/ 4.76 cm^2, 10 mg/ 9.52 cm^2, 15 mg/14.29 cm^2 and 20 mg/19.05 cm^2) in children and adolescents 6 to 17 years of age with ADHD.

The study will consist of a four-week screening period, a one-week wash-out period (if applicable), a five-week open-label, step-wise dose optimization period and two-week double blind randomized crossover treatment period with weekly classroom assessments and a safety follow-up by telephone 7 - 10 days after last dose of study drug.

**Screening Period (Visit -1):** Screening procedures may be performed within four weeks prior to the Dose Optimization Period of the study.

**Washout Period:** Eligible subjects will undergo a 72 hour wash-out period if applicable.

**Baseline Visit (Day 0, Visit 0):** Eligible subjects will return to the clinic on Day 0 for baseline assessments. Subjects who continue to meet the eligibility criteria will be entered into the open-label Dose Optimization period.

**Dose-Optimization Period [Day 1 to Day 35; Visit 1 (Day 7 ±3 days), Visit 2 (Day 14 ±3 days), Visit 3 (Day 21 ±3 days), Visit 4 (Day 28 ±3 days) and Visit 5 (Day 35 ±2 days)]:**

Following Screening Period and Washout Period (if applicable), eligible subjects will enter the open-label Dose-Optimization Period, during which they will begin receiving d-ATS followed by evaluation for efficacy and tolerability of that dosage approximately 7 days later. Dosage will

Amendment 4: Version 5.0 May-08-2013

Amendment 3: Version 4.0 December-11-2012

Amendment 2: Version 3.0 October-31-2012

Amendment 1: Version 2.0 August-02-2012

Final Protocol May-25-2012

be initiated at 5 mg/ 4.76 cm^2 d-ATS and adjusted to the next available dose at weekly intervals, until optimal dose is reached. Optimal dose will be defined as the dose that will produce a reduction in ADHD RS-IV score  $\geq 30\%$  and CGI-Improvement (CGI-I) score of 1 or 2 and has tolerable side effects.

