Tolerability will be determined by the investigator, based on review of AEs and clinical judgment. Once reached, the optimal dose will be maintained for the remainder of the Dose-Optimization Period. Investigator can increase the current dose to provide additional symptom control. One dose reduction will be permitted if the subject experiences unacceptable tolerability of the current dose.

Subjects will be discontinued if they are unable to tolerate d-ATS or cannot reach their optimal dose by Week 5. If the subject has reached their optimal dose, then at the discretion of a medically qualified investigator, one dose reduction per participant may occur during the dose optimization period for safety reasons. However if the current dose is intolerable and the subject has never reached their optimal dose, the subject would be discontinued from the study. A dose increase may occur at visit 4 if no prior dose has met criteria for optimal response and the current dose is well tolerated as deemed by a medically qualified investigator. The dose used during the week 5 visit will be the dose that the subject is randomized to during the Double-Blind Treatment Period.

During Visit 5 (Day 35  $\pm$  2 days), subjects will attend a half-day practice laboratory school with analog classroom sessions to become familiar with classroom schedules and procedures. Three SKAMP assessments will be performed, and 3 practice PERMP tests will be given during the practice session.

Subjects will return to the clinic for evaluations and dose adjustments on Visit 1 (Day 7  $\pm$  3days), Visit 2 (Day 14  $\pm$  3days), Visit 3 (Day 21 $\pm$  3days), Visit 4 (Day 28  $\pm$  3days) and for evaluations (no further dose adjustments) and randomization on Visit 5 (Day 35)  $\pm$  2days (see schematic below). Site personnel will contact subjects by telephone on Day 4, Day 11, Day 18, Day 25 and Day 32 or midway between visits. Subjects/parents/caregivers will be instructed to complete a daily dosing diary and a daily dermal diary. All end of study procedures will be completed for subjects who are early discontinuations from the study.

Visit/Week	d-ATS	Evaluations
Visit 0/Week 1	5 mg d-AMP/ 4.76 cm  patch (4-10doses)	ADHD RS-IV, CGI-Improvement (CGI-I) and AEs and PERMP

Amendment 4: Version 5.0 May-08-2013

Amendment 3: Version 4.0 December-11-2012

Amendment 2: Version 3.0 October-31-2012

Amendment 1: Version 2.0 August-02-2012

Final Protocol May-25-2012

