3. STUDY DESIGN

This is a randomized, double-blind, cross-over, placebo controlled study to evaluate the safety and efficacy of d-ATS in children and adolescents 6 to 17 years of age with Attention Deficit Hyperactivity Disorder (ADHD).

The study will consist of a four-week screening period, a 72-hour wash-out period (if applicable), a five-week open-label, step-wise dose optimization period and two-week double blind randomized crossover treatment period with weekly classroom assessments and a safety follow-up by telephone 7 - 10 days after last dose of study drug. Approximately 90 subjects will be randomized at 3 sites.

Screening Period (Visit -1): Screening procedures may be performed within four weeks prior to the Dose Optimization Period of the study.

Washout Period: Eligible subjects will undergo a 72 hour wash-out period if applicable.

Baseline Visit (Day 0, Visit 0): Eligible subjects will return to the clinic on Day 0 for baseline assessments. Subjects who continue to meet the eligibility criteria will be entered into the open-label Dose Optimization period.

Dose-Optimization Period [Day 1 to Day 35; Visit 1 (Day 7), Visit 2 (Day 14), Visit 3 (Day 21), Visit 4 (Day 28) and Visit 5 (Day 35)]: Following Screening Period and Washout Period (if applicable), eligible subjects will enter the open-label Dose-Optimization Period. Optimal dose will be defined as the dose that will produce a reduction in ADHD RS-IV score $\geq 30\%$ and CGI-Improvement (CGI-I) score of 1 or 2 and has tolerable side effects. Tolerability will be determined by the investigator. The Investigator can increase the current dose to provide additional symptom control. One dose reduction will be permitted if the subject experiences unacceptable tolerability of the current dose.

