7.7.2 Deaths and Serious Adverse Events

The following summaries will be presented separately for the Dose-Optimization Period and the double-blind Treatment Period by the dose being taken at the onset of the events and by MedDRA SOC, and preferred term:

- Serious adverse events (SAEs)
- Treatment-related SAEs

All data for serious adverse events and deaths will be listed

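### The open-label adverse event tables by dose at onset give crude counts and percentages although time at dose is unequal by design, so columns can differ when dose has no effect.

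*SAP*

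**What the plan says.** SAP 7.7.1 lists the treatment-emergent event summaries that will be "presented separately for the Dose-Optimization Period and the double-blind Treatment Period by the dose being taken at the onset of the events", by system organ class and preferred term. SAP 7.7.2 applies the same layout to serious events: "by the dose being taken at the onset of the events and by MedDRA SOC, and preferred term". The content of every such table is fixed in SAP 7.7.1: "All summaries of adverse events will consist of the number of events and the numbers and percentages of subjects who had the events being summarized". No rate per unit of exposure is planned, and the by-dose sentences do not say which children form the denominator of a dose column. A separate sentence in SAP 7.7.1 gives pooled summaries "on all subjects combined during the Dose-Optimization Period and by treatment arm during the double-blind Treatment Period".

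Exposure is set by Protocol 5.1. Dosing starts at 5 mg and is "adjusted to the next available dose at weekly intervals, until optimal dose is reached". Then: "Once reached, the optimal dose will be maintained for the remainder of the Dose-Optimization Period". The period is given in SAP 3 as "Dose-Optimization Period [Day 1 to Day 35".

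SAP 7.4.1 summarizes dose at each visit, and duration of dosing by visit and overall, but not duration by dose. SAP 7.7 plans no inferential statistics for safety. SAP 7.7.1 assigns an event to 5 mg when its dose at onset cannot be determined.

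**The concern.** A percentage of subjects with an event depends on how long they were watched. Here the columns are doses, and the time spent in a column depends on whether the child passed through that dose or stayed on it. Two columns with the same daily risk can therefore show different percentages.

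The safety of d-ATS is a primary objective. The open-label period is the only part of the trial in which one child may receive several strengths; in the double-blind weeks each child has about 7 days of active drug at a single dose. The by-dose table will be read as the trial's picture of tolerability by dose, even though it is only descriptive. Difference in exposure time could then be taken for a dose effect, or could mask one.

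**Working it through.** The plan states no figure for adverse events by dose, so there is none to reproduce. The check asks what the table would show if dose had no effect.

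**Inputs from the documents.** Open-label period of 35 days (SAP 3); weekly steps and then a hold at the optimal dose (Protocol 5.1). Nominal days at dose follow by subtraction: a child who stays has T = 35, 28, 21 or 14 days at 5, 10, 15 or 20 mg, and a child who passes through has 7.

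**Assumptions not in the documents.** A constant hazard h per day, the same at every dose (range 0.005 to 0.05), and the split of final doses.

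**Formulas.** With s the share staying on a dose and r the share ever on it:
- Mean days at dose = [s·T + (r − s)·7] / r
- Crude percentage among those exposed = [s(1 − exp(−hT)) + (r − s)(1 − exp(−7h))] / r

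**Worked case, h = 0.01, split 10/30/35/25.** The building blocks are 1 − exp(−0.07) = 6.76%, 1 − exp(−0.14) = 13.06%, 1 − exp(−0.21) = 18.94%, 1 − exp(−0.28) = 24.42% and 1 − exp(−0.35) = 29.53%.
- 5 mg: 0.10 × 29.53 + 0.90 × 6.76 = 9.0%
- 10 mg: (0.30 × 24.42 + 0.60 × 6.76) / 0.90 = 12.6%
- 15 mg: (0.35 × 18.94 + 0.25 × 6.76) / 0.60 = 13.9%
- 20 mg: 13.1%

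**Other splits at h = 0.01, children exposed as denominator:**

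| Final-dose split | Mean days at 5/10/15/20 mg | Crude % at 5/10/15/20 mg |
|---|---|---|
| 10/30/35/25 | 9.8 / 14.0 / 15.2 / 14.0 | 9.0 / 12.6 / 13.9 / 13.1 |
| 5/15/30/50 | 8.4 / 10.3 / 12.2 / 14.0 | 7.9 / 9.5 / 11.3 / 13.1 |
| 25/25/25/25 | 14.0 at each dose | 12.5 / 12.6 / 12.9 / 13.1 |
| 40/30/20/10 | 18.2 / 17.5 / 16.3 / 14.0 | 15.9 / 15.6 / 14.9 / 13.1 |

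**Range.** I took all 969 splits with at least 5% at each dose, in steps of 5%. The gap between the highest and lowest column has this distribution:

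| h per day | Median gap (points) | Range (points) | Splits with gap over 5 points |
|---|---|---|---|
| 0.005 | 3.3 | 0.2 to 8.0 | 16% |
| 0.01 | 6.1 | 0.5 to 14.7 | 73% |
| 0.02 | 10.3 | 1.1 to 24.8 | 94% |
| 0.05 | 18.1 | 2.1 to 38.3 | 99% |

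The grid weights all splits equally and is not a forecast. For rare preferred terms the gap in points shrinks, but the ratio between columns tends to the ratio of mean days: 15.2 / 9.8, about 1.55, in the worked case.

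**What the rate does and does not repair.** Under constant hazard, events per 100 patient-days equal 100h at every dose for every split, so the exposure artefact disappears. Now suppose that events fade with time on drug, with an assumed hazard of 0.04·exp(−d/14) on day d, no dose effect and the 10/30/35/25 split.
- 5 mg: expected events are 0.10 × 0.56(1 − exp(−2.5)) + 0.90 × 0.56(1 − exp(−0.5)) = 0.250 over 9.8 days, or 2.55 per 100 patient-days.
- 20 mg: 0.56(exp(−1.5) − exp(−2.5)) = 0.079 over 14 days, or 0.56 per 100 patient-days.

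First-7-day incidence falls too, from 1 − exp(−0.220) = 19.8% at 5 mg to 1 − exp(−0.049) = 4.8% at 20 mg. Neither measure separates dose from time.

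**Dependence on the protocol text.** The 7 and 35 days are nominal. The schedule in Protocol 5.1 allows 4 to 10 doses per step, and dropouts have less exposure. The Week 2 row of that schedule gives 10 mg without the exemption for children already at optimal dose that the 15 and 20 mg rows carry. Read literally, everyone has 7 days at 5 mg and the longest nominal stay is 28 days. Exposure is still unequal: a 0/20/40/40 split gives 7.0, 11.2, 14.0 and 14.0 days, and 6.8, 10.3, 12.9 and 13.1% at h = 0.01.

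**The case against.** The strongest reply is that comparing doses is not an objective. The table is descriptive, no safety inference is planned, and open-label safety is also pooled over all subjects. Dose at each visit is summarized and all dosing data are listed, so a reader could rebuild approximate child-weeks per dose. The worked gap is just under 5 points. With an assumed 100 children on 5 mg and 60 on 15 mg, its standard error is √(0.09 × 0.91/100 + 0.139 × 0.861/60), about 5 points, treating the columns as independent. All of this stands and limits the weight of the point. It does not make crude percentages the better display, because the reconstruction cannot be done from the adverse event table itself.

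A second reply is that the model is idealized. Protocol 5.1 also allows an increase for more symptom control and one reduction, and steps vary in length. That is true, and it makes actual time at dose more variable.

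A third is that a person-time rate isolates dose only if the hazard is constant. This also stands: the fading-hazard case shows a steep false fall. The rate must therefore sit beside the crude percentage and cannot replace it.

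A reader might infer that the table must show a false rise with dose. The documents do not support that: an equal split is almost flat and 40/30/20/10 falls slightly. A reader might also infer a false fall at the top dose by dividing every column by the whole Safety population (9.0, 11.4, 8.3 and 3.3% in the worked case). The SAP does not state that denominator for the by-dose tables. The phrase about all subjects combined belongs to the pooled summary, and for double-blind summaries SAP 7 sets header numbers to the subjects receiving the treatment. Table shells that might settle the column N are not in the text available. On this the main text lacks detail; it does not contain an error.

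**Conclusion.** The point holds in a limited form. The open-label by-dose tables in SAP 7.7.1 and 7.7.2 give crude counts and percentages over unequal exposure. With no dose effect and a constant hazard, the columns can differ. At 1% per day, 73% of the assumed splits give a gap above 5 points, with a median gap of 6.1; at 0.5% per day only 16% do.

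Size and direction rest on the hazard and the final-dose split, neither of which the documents give, and on nominal days at dose. It would go too far to say that the table measures only exposure, or that the trial's safety conclusion is undermined. One descriptive dose-tolerability display is affected. The double-blind d-ATS versus placebo comparison, with about 7 days on each treatment, and all efficacy results are untouched. The change is worth making because it is cheap and gives a better display.

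**What to change.** In the open-label by-dose tables of SAP 7.7.1 and 7.7.2:
- define the column N as the children who wore that dose;
- show total patient-days at that dose;
- beside the crude percentages, add events per 100 patient-days and incidence in the first 7 days at that dose (or up to the next visit, if sooner);
- add a footnote that dose is confounded with time on drug and with having tolerated lower doses, so that neither the percentages nor the rates isolate a dose effect.

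The cost is a few table columns and some SAP wording. The dosing diaries and the dose recorded at each visit already supply the data.

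The protocol text that determines exposure by dose must also be reconciled. The Week 2 row of the schedule in Protocol 5.1 conflicts with the statement there that the optimal dose is maintained. Protocol 5.1 allows an increase at Visit 4 under stated conditions, whereas Protocol 5.3.4.2 allows only a reduction at that visit. Which reading is right is for the sponsor to settle.

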7.7.2 Deaths and Serious Adverse Events

The following summaries will be presented separately for the Dose-Optimization Period and the double-blind Treatment Period by the dose being taken at the onset of the events and by MedDRA SOC, and preferred term:

- Serious adverse events (SAEs)
- Treatment-related SAEs

All data for serious adverse events and deaths will be listed

7.7.3 Laboratory Data

A central laboratory will be used to analyze all blood and urine samples with the exception of the urine pregnancy tests. Laboratory data is only collected at Screening and Visit 7/End of Study (or Early Termination visit). For analyses of laboratory data, 'baseline' refers to the data collected at screening. The clinical laboratory assessment will consist of the following:

Hematology: hemoglobin, hematocrit, white blood cell count, red blood cell count, platelet count, basophils, neutrophils, bands, lymphocytes, monocytes, and eosinophils.

Serum Chemistry: total bilirubin, alkaline phosphatase, alanine transaminase, aspartate transaminase, creatine phosphokinase, lactate dehydrogenase, blood urea nitrogen, creatinine, glucose, total protein, albumin, sodium, potassium, chloride, calcium, inorganic phosphorus, and Hemoglobin A_{1c}.

Urinalysis: specific gravity, pH, protein, glucose, ketones, bilirubin, and blood.

Urine drug screen and cotinine (screening only)

Summary statistics of raw data and change from baseline to End of Study values for each laboratory parameter will be presented by treatment arm. Data will be summarized as appropriate to the variable type.

For change from baseline summaries, subjects with an undefined change from baseline, because of missing baseline data, will be excluded. Individual Subject Changes will be identified through shift tables. Shift tables will be presented for each laboratory parameter with counts and percentages of subjects, by treatment arm, for shift (change) from baseline, using the normal ranges from the central laboratory.

Where multiple results are provided for a parameter the first set of observations will be included in the summaries, all data will be listed. Similarly, if both automated and manual differential results are provided for a visit then the automated differentials will be summarized, all will be listed.

Laboratory data from unscheduled visits will be listed but will not be included in any summaries. Results of urine pregnancy results will be listed but will not be included in any summaries.

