### ***5.3.3 Baseline (Visit 0, Day 0)***

Subjects who continue to meet the eligibility criteria will report to the clinic on Day 0 (Visit 0) and the following procedures will be performed:

1. Record any AEs or concomitant therapy since previous visit.
2. Obtain ADHD-RS-IV score and confirm eligibility.
3. Obtain weight and vital signs.
4. Perform urine pregnancy testing on all female subjects of child-bearing potential.
5. C-SSRS (Children's Baseline version) will be administered by a trained staff member.
6. Perform CGI-S.
7. Perform a 12-lead electrocardiogram (ECG).

Amendment 4: Version 5.0 May-08-2013

Amendment 3: Version 4.0 December-11-2012

Amendment 2: Version 3.0 October-31-2012

Amendment 1: Version 2.0 August-02-2012

Final Protocol May-25-2012

8. Perform two PERMPs at demonstrated level.
9. Demonstrate patch application and provide instructions on correct application to parent/caregiver/subject.
10. Contact IVRS/IWRS to obtain study medication pack number, and dispense study medication.
11. Parents/caregivers/subjects will be instructed to apply patches once daily in the morning beginning the next day and to comply with the study drug dosing regimen.
12. Parents/caregivers/subjects will be instructed to complete their daily dosing diary and daily dermal evaluation diary
13. Parents/caregivers will be instructed on completion of the CPRS-R:S and instructed on which days to complete the assessment.
14. Parents/caregivers/subjects will be informed as to the time and date of next study visit and the importance of having the subject keep that visit.
15. Parents/caregivers/subjects will be instructed to save all unused and used patches and bring them to their clinic visits. Parents/caregivers/subjects will be instructed to save all the used patches in the supplied container.
16. Parents/caregivers/subjects will be instructed to call the site personnel to report any AEs and concomitant therapy.
17. Dismiss from clinic.

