#### ***8.4.2 Clinical Laboratory Test Values***

Summary statistics of raw data and change from baseline values to End of Study values for each laboratory parameter will be presented by treatment group and time point. Data will be summarized as

Amendment 4: Version 5.0 May-08-2013

Amendment 3: Version 4.0 December-11-2012

Amendment 2: Version 3.0 October-31-2012

Amendment 1: Version 2.0 August-02-2012

Final Protocol May-25-2012

appropriate to the variable type. For change from baseline summaries, patients with an undefined change from baseline, because of missing baseline data, will be excluded. Individual Patient Changes will be identified through shift tables. Shift tables will be presented for each laboratory parameter with counts and percentages of patients, by treatment group and time point, for shift (change) from baseline, using the normal ranges from the central laboratory.

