7. STATISTICAL METHODS

Summaries will be presented for the SP population for all subjects combined during the Dose-Optimization Period of the study. During the double-blind Treatment Period of the study, summaries will be presented for the FAS, Completers, and SP populations by treatment (i.e., d-ATS and placebo, with all d-ATS dose levels combined), and some tables by treatment and treatment sequence. Subjects are intended to receive both treatments during the double-blind cross-over period of the study, so summaries for Visits 6 and 7 will be combined, with subjects contributing data to both treatment columns for the combined time point. As a result, the numbers of subjects in each treatment arm in the header of these summaries will reflect the total number of subjects receiving the treatment, and the number of subjects contributing data for each visit will be presented in the body of the table.

Early termination visits will be mapped to the next scheduled visit for inclusion in summary tables, where appropriate. For example, a subject who terminates after Visit 3 (e.g., has assessments at Visits 1 - 3 and early termination assessments) would have assessments from early termination mapped to the next scheduled visit for each assessment. Different assessments may be mapped to different visits; in this example, most assessments would be mapped to Visit 4, ECG would be mapped to Visit 5 as no ECG assessments are scheduled to be performed at Visit 4. This mapping is considered part of the observed values, and will be conducted before any summaries or analyses are performed on observed values. Similarly, it will be conducted before any scoring algorithm is applied. Listings will present early termination data as the mapped visit, as well as under 'ET' Visit as well.

Unless otherwise noted, categorical variables will be summarized using counts and percentages. Percentages will be rounded to one decimal place, except 0% and 100% will be displayed without any decimal places. Continuous variables will be summarized using the number of observations (n), mean, standard deviation (SD), median, minimum, and maximum. All analyses will use SAS® version 9.1 or higher.

All raw data will be presented to the original number of decimal places. The means and medians will be presented to 1 more decimal place than the raw data. The standard deviations will be presented to 2 more decimal places than the raw data.

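### The laboratory tables split change from screening into d-ATS and placebo columns, but both columns are sampled after nominally 42 days of d-ATS

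*SAP*

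**What the plan says.** SAP 7.7.3 fixes the presentation: "Summary statistics of raw data and change from baseline to End of Study values for each laboratory parameter will be presented by treatment arm". The shift tables give counts and "percentages of subjects, by treatment arm, for shift (change) from baseline, using the normal ranges from the central laboratory". Protocol 8.4.2 has the same split, with raw values and changes "for each laboratory parameter will be presented by treatment group and time point".

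SAP section 7 defines the double-blind columns: summaries are "by treatment (i.e., d-ATS and placebo, with all d-ATS dose levels combined), and some tables by treatment and treatment sequence". It does not name the tables that also get the sequence split.

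On sampling, SAP 7.7.3 says "Laboratory data is only collected at Screening and Visit 7/End of Study (or Early Termination visit"), and "For analyses of laboratory data, 'baseline' refers to the data collected at screening". The protocol synopsis places the Visit 7 draw before discharge on Day 49, and protocol 5.3.5.3 limits laboratory collection in the double-blind period to that day.

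On exposure, SAP section 3 describes an open-label "Dose-Optimization Period [Day 1 to Day 35". Under protocol 5.3.3, families at Visit 0 are "instructed to apply patches once daily in the morning beginning the next day", which is Day 1. Randomization is then 1:1 to one week of d-ATS and one week of placebo in either order (SAP 3 and 3.2).

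**The concern.** In a two-column safety table most readers take placebo as the untreated reference. Here the change runs from before any drug to after about six weeks of drug in both columns. If a parameter moved by the same amount in each, the table would look like a background shift with no drug effect, although both groups had been treated. Safety is one of the two primary objectives (protocol 4, SAP 2).

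Two features of the plan add to this. First, SAP section 7 justifies treatment columns by combining Visits 6 and 7, so that each child contributes to both. Laboratory data have no Visit 6 sample, so each completer enters one column only and no within-child comparison exists.

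Second, SAP section 7 maps early-termination results to the next scheduled visit for that assessment. For laboratory tests that visit is Visit 7. A child who stops during open-label dosing was never randomized and has no arm, and no rule says where that child's only post-drug sample goes.

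**Working it through.** **Timeline.** Five open-label weeks plus two double-blind weeks: 5 × 7 + 2 × 7 = 49, which matches the plan's Day 49. The plan gives no cumulative exposure figure, so it is derived here.

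**d-ATS days before the Visit 7 sample, nominal schedule.**
- d-ATS then placebo: Days 1–35 (35) + Days 36–42 (7) = 42, followed by 7 days of placebo.
- Placebo then d-ATS: Days 1–35 (35) + Days 43–49 (7) = 42.
- Difference between the columns: 42 − 42 = 0 days.

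**Visit 5 window (Day 35 ± 2, protocol 5.1).**
- If Visits 6 and 7 stay on Days 42 and 49, d-ATS-then-placebo has 42 days and placebo-then-d-ATS has 40 to 44.
- If Visits 6 and 7 move with Visit 5, both have 40 to 44.

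**Start of dosing.** Protocol 7.2 describes dosing as starting at Visit 1 (Day 7), whereas protocol 5.3.3 and SAP 3 point to Day 1. These sections must be reconciled. On the Visit 1 reading, exposure is Days 7–35 (29) + 7 = 36 in both sequences, and the columns are still equal.

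**Who is in each column.** With 74 planned completers and 1:1 allocation, about 74 / 2 = 37 completers fall under placebo. The table's actual denominator is the Safety Population, so this is only a guide. A randomized child who stops in Week 6 on placebo has still had nominally 35 days of d-ATS, so no child in the placebo column is unexposed.

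**How much the contrast could understate an effect.** The documents give no reversal rates, so this step is an illustration on an assumption. Suppose the drug effect builds up and wears off at a first-order rate with half-life h days. After d days the effect is E_new = T + (E_old − T) × 2^(−d/h), with T = 1 on drug and T = 0 off. The d-ATS column is 35 days on, 7 off, 7 on. The placebo column is 42 on, 7 off.

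For h = 7:
- d-ATS column: 1 − 2^(−5) = 0.969, then 0.484, then 1 − (1 − 0.484) × 0.5 = 0.742.
- Placebo column: 1 − 2^(−6) = 0.984, then 0.492.
- Ratio: 0.492 / 0.742 = 66%.

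| h (days) | d-ATS column | Placebo column | Placebo as share of d-ATS |
|---|---|---|---|
| 1 | 0.992 | 0.008 | 1% |
| 3 | 0.841 | 0.198 | 24% |
| 7 | 0.742 | 0.492 | 66% |
| 14 | 0.705 | 0.619 | 88% |
| 30 | 0.551 | 0.528 | 96% |
| 60 | 0.361 | 0.355 | 98% |

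Fast-reversing parameters separate well. Slow ones look almost the same in both columns.

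**The case against.** The strongest reply is that nothing is removed. Baseline is screening, before any d-ATS, so a persistent drug effect shows as a change from baseline in both columns and in both shift tables. All laboratory values are listed, clinically significant ones are recorded as adverse events (protocol 6.14), and no inferential statistics are planned for safety (SAP 7.7). The columns are also a randomized comparison of children on drug with children one week off it, which is informative for parameters that reverse quickly. For completers, relabelling by sequence gives the same figures under new headings. All of this stands.

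A reader might go further and infer that the layout will conceal a laboratory signal, or that the split is uninformative. The documents support neither reading. Only the between-column contrast is weakened, by an amount that depends on reversal rates they do not give, and the reader must also take placebo to mean unexposed.

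Two other replies carry less weight. SAP 7.7 limits the arm split to where it is applicable, but 7.7.3 then applies it to laboratory data. SAP 7.7 also pools Dose-Optimization safety data, which could cover open-label early-termination samples, but the mapping rule sends them to Visit 7 and the conflict is not resolved.

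The table shells are not in the text available for this review, so an overall column or a sequence split there cannot be excluded. No available section specifies a pooled screening-to-End-of-Study laboratory table or warns about prior exposure.

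**Conclusion.** The point holds as one of labelling and missing pooling. On the nominal schedule the two columns differ by 0 days of cumulative d-ATS (42 against 42). They differ only in whether the last 7 days were on or off drug. The placebo column cannot serve as an unexposed control, and reading it as one would attribute d-ATS-exposed change to placebo. The contrast can understate slowly reversing effects; how far is unknown, and the half-life table is an illustration only.

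The 42 days assume a completer on schedule. The window gives 40 to 44 and early terminators have fewer. Equality of the columns does not depend on which dosing start day is correct. The finding also assumes that the shells contain no pooled column.

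**What to change.** Make the main laboratory output a pooled screening-to-End-of-Study change and shift table for all d-ATS-exposed subjects in the Safety Population. Every child's first study drug is d-ATS, so this is the whole Safety Population with a post-baseline sample. State that early-termination samples taken before randomization are included there.

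Keep the current split as a secondary table, relabelled by sequence or by last treatment received (d-ATS last, placebo last). Add a footnote that all children in both columns had prior open-label d-ATS. The pooled table is itself an uncontrolled before-and-after summary and should be described as such.

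SAP 1.1 currently declares no changes from the protocol, so record the change there and align protocol 8.4.2. Protocol 9.3.2 allows changes in statistical methods to be documented as an administrative change. No new data or procedures are needed. The cost is one extra set of descriptive tables and a documented departure from the protocol text.
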